10.2.2.2. Subgroup Analyses

Potential effect modification will be examined by including interaction terms between interventions and baseline factors such as gender, race, age, coping style, depression, and anxiety. For baseline factors with statistically significant interactions, intervention effects will be reported by subgroups.

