10.2. Statistical Considerations for the Phase 1 Randomization

10.2.1. Sample Size and Power Analysis for the Primary Objective

The primary objective for Phase 1 is to compare changes from baseline to 12 weeks in the BPI Interference scores between the PCST and Usual Care groups. The null hypothesis is that the change in BPI Interference score is the same in the PCST and Usual Care groups.

Table 10.2 depicts the minimum detectable difference between the PCST and Usual Care groups in the change in BPI Interference score, for a power of 90%, a type 1 error of 5%, an attrition rate of 20%, standard deviations of change of 2 and 3, a total number of participants ranging from 480 – 800 (participant numbers per Clinical Center ranging from 60 to 100), intra-class correlation coefficients of 0 and 0.02, and an interim analysis of one look at 50% information time. Details of the interim analysis are described in **Section 10.2.3**. All calculations are based on two-sample t tests. As one example, if the total sample size is 640, the number of participants per Clinical Center is 80, the ICC is 0 (i.e., no clustering effect), and the standard deviation of the change in BPI Interference score is 2, the BPI Interference score for PCST would need to decrease by at least 0.62 points if the change in BPI Interference score for Usual Care were 0 (**Table 10.2, Row #2**). As another example, again using the parameters in **Table 10.2, Row #2**, the change in the BPI Interference score would need to decrease by 1.02 in the PCST group if the score decreased by 0.40 in the Usual Care group.

Table 10.2. Minimum Detectable Differences between the PCST and Usual Care Groups in the Change from Baseline to Week 12 in the BPI Interference Score

Row	Total N	Clinical Center n	ICC	Minimum Detectable Between-Group Difference in Change in BPI Interference Score ¹	
				If SD = 2	If SD = 3
1	800	100	0	0.56	0.83
2	640	80	0	0.62	0.93
3	480	60	0	0.72	1.08
4	800	80	0.02	0.73	1.10
5	640	80	0.02	0.78	1.17
6	480	60	0.02	0.86	1.29

¹Effect sizes determined for a power of 90%, at a type 1 error of 5%, an attrition rate of 20%, standard deviations of change of 2 and 3, and an interim analysis of one look at 50% information time, using two-sample t tests.

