10.2.1.1. Rationale for the Selected Sample Size

The trial will aim to enroll 640 participants. Based on the minimum detectable differences in changes of BPI Interference scores under a range of assumptions provided in **Table 10.2**, for the primary objective of comparing PCST with Usual Care in Phase 1, this sample size will allow detection of a difference in the change in BPI Interference score of 0.62 if there is no intra-cluster correlation and a standard deviation of change of 2, or 1.17, under the conservative assumptions of an intra-cluster correlation coefficient (ICC) of 0.02 and a standard deviation of change of 3 (which is larger than the SD of change observed in studies of chronic pain in non-ESRD patient populations⁵⁷). Based on a review of the literature, the Initiative on Methods, Measurement, and Pain Assessment in Clinical Trials identified 1 as the minimal clinically important change *for individuals* on the BPI Interference scale.⁵⁷ However, this group also recognized a critical tenet of randomized trials with between group comparisons: "...criteria for clinically important change in individuals cannot be directly applied to the evaluation of clinically important group differences." Determination of the importance of group differences must be established in the broader context of the disease being treated, the currently available treatments, and the overall risk-benefit evaluation of the treatment. Our proposed sample size will allow us to detect a between-group difference *as small as* the ranges listed above. We hypothesize that the actual observed difference will be larger because we are testing an adaptation of an evidence-based intervention that has had moderate effect sizes in other populations and settings.²⁷⁻²⁹

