10.2.2. Statistical Analyses

General Approach. The following descriptive statistics will be used: number of observations, mean, standard deviation, median, minimum and maximum for continuous variables; frequencies and proportions for categorical variables; number of events and rates for count variables. Results will be reported in accordance with the extended CONSORT guidelines for pragmatic clinical trials⁶¹ using two-sided statistical tests and confidences intervals. For all analyses, the overall level of significance will be set at 0.05. Methods for multiple comparisons such as Bonferroni, false discovery, or others, will be implemented to maintain the overall 0.05 level of significance. All analyses will be adjusted for site and the presence or absence of opioid use using the criteria provided in **Section 5.3**. All analyses will be performed using SAS v9.4 (SAS Institute, Cary, NC) or the latest version of R (currently 3.6.1; <https://cran.r-project.org/>).

Baseline Descriptive Statistics. Randomization adequacy will be assessed by comparing the distributions of baseline demographic and clinical characteristics between the PCST and Usual Care groups. Comparability for continuous variables will be examined graphically and by summary statistics: mean, standard deviation, median, minimum, and maximum for continuous variables, and frequency and proportion for categorical variables. If statistically and/or clinically meaningful differences are found in baseline characteristics (i.e., baseline characteristics are not balanced between the PCST and Usual Care groups), sensitivity analyses will be conducted with covariate adjustment.

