10.2.2.1. Analyses of the Primary Endpoint for the Phase 1 Randomization

Question 1 (Table 10.1): Does a PCST intervention consisting of weekly, live, coach-led sessions improve outcomes at 12 weeks?

Question 1 addresses the primary trial hypothesis. The primary efficacy endpoint, the change in BPI Interference between baseline and 12 weeks, and will be analyzed using a linear mixed effects model.⁶² The linear mixed effects model will include fixed effects of intervention, time, and interactions between intervention and time, taking into account the repeated measures over time and clustering of recruitment sites via random effects. All repeated measures of the BPI Interference scores at baseline and 12 weeks will be included in the model as the dependent variable. The linear mixed effects model is expressed as

$$y_{ijk} = \beta_0 + \beta_1 X_{ij} + \beta_2 I(T_{ijk} = 12) + \beta_3 X_{ij} I(T_{ijk} = 12) + \gamma^T \mathbf{W}_{ij} + \theta_i + \alpha_{ij} + \varepsilon_{ijk},$$

where y_{ijk} is the BPI Interference score for participant ij ($i = 1, 2, \dots, 14$; $j = 1, 2, \dots, n_i$; n_i is number of participants from recruitment site i) at time point k ($k = 1, 2$), X_{ij} is the binary intervention indicator ($X_{ij} = 1$ if PCST; $X_{ij} = 0$ if Usual Care) for participant ij , T_{ijk} is the study weeks for participant ij at time point k ($T_{ij1} = 0$ and $T_{ij2} = 12$), $I(\cdot)$ is an indicator function returning 1 (0) if the event is true (false), \mathbf{W}_{ij} is a vector of baseline measures, including the stratification factors, for participant ij , β 's and γ are regression parameters for the fixed effects, θ_i and α_{ij} are the regression parameters for the random effects for recruitment site i and participant ij , respectively, and ε_{ijk} is the random error for participant ij at time point k . Model diagnostics will be conducted to examine the assumption of normality. If there are potential violation of the assumptions, transformations of the data beginning with a log transformation will be explored. The primary efficacy estimand is the contrast of PCST and Usual Care for the change at the 12-week time point; i.e., β_3 . Differences in changes, their 95% confidence intervals, and p-values will be presented.

Question 2 (Table 10.1): Does a PCST intervention consisting of weekly, live, coach-led sessions for 12 weeks followed by IVR for 12 weeks improve outcomes at 24 weeks?

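### For continuous outcomes, Section 10.2.2.2 names intervention × factor as the subgroup test, but the 12-week effect is intervention × time; taken literally, the named term tests a diluted quantity

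*Combined protocol and SAP*

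**What the plan says.** Section 10.2.2.2 (Subgroup Analyses) has two sentences. The first is "Potential effect modification will be examined by including interaction terms between interventions and baseline factors", followed by examples: demographic factors, coping style, depression and anxiety. The second is "For baseline factors with statistically significant interactions, intervention effects will be reported by subgroups". There is no equation, no named coefficient and no mention of time.

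Section 10.2.2.1 is explicit about the primary model. "The linear mixed effects model will include fixed effects of intervention, time, and interactions between intervention and time", and "All repeated measures of the BPI Interference scores at baseline and 12 weeks will be included in the model as the dependent variable". It then defines the effect: "The primary efficacy estimand is the contrast of PCST and Usual Care for the change at the 12-week time point", which is β3, the coefficient on X·I(T = 12). The Week 24 and Week 36 models have the same form, with the effect carried by the intervention × visit coefficient for the visit in question. Section 10.2.3.2 (Analyses of the Secondary Endpoints) applies similar models to the continuous secondary outcomes.

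**The concern.** In this model the coefficient on intervention alone, β1, is the difference between arms at baseline, which randomisation makes zero in expectation. The treatment effect sits only in the intervention × time term. An interaction of intervention with a baseline factor therefore modifies the arm difference averaged over all visits, baseline included. It does not modify the 12-week effect. Unless a three-way term is added, β3 is forced to be the same in every subgroup, so the model cannot produce the subgroup effects that the second sentence of 10.2.2.2 promises.

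The test also decides what is reported, since subgroup effects appear only for factors that pass it. A test aimed at a diluted quantity would miss real modification more often than it needs to. Its coefficient would also not equal the difference between subgroup values of β3.

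**Working it through.** **The plan's own figures.** The plan gives no power for the subgroup tests, so only the main-effect figures can be reproduced. Inputs (Sections 10.2.1, 10.2.1.1 and 10.2.2): "The trial will aim to enroll 640 participants"; "for a power of 90%, a type 1 error of 5%, an attrition rate of 20%, standard deviations of change of 2 and 3"; "using two-sided statistical tests and confidences intervals"; interim inflation 1.173; design effect 1 or 1.574.

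- ICC 0: n per arm = 320 × 0.8 / 1.173 = 218.2. Detectable difference = 2 × √(2/218.2) × (1.960 + 1.282) = 0.62, as in Table 10.2, row 2.
- ICC 0.02: n per arm = 320 / 1.574 × 0.8 / 1.173 = 138.7 (stated: about 139). With SD 3 the difference is 1.17, as in row 5.

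**What each term estimates.** Let d be the true modification at Week 12, with none at baseline. Let σ be the SD of the score at each visit (taken as equal) and ρ the correlation between the two visits. With complete data and a participant random intercept:

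- Intervention × factor is the least-squares interaction on the participant mean (y0 + y12)/2. It estimates (0 + d)/2 = d/2, with variance proportional to σ²(1 + ρ)/2.
- Factor × intervention × I(T = 12) is the least-squares interaction on y12 − y0. It estimates d, with variance proportional to 2σ²(1 − ρ).

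Ratio of expected z statistics, two-way over three-way: (½ / √[(1 + ρ)/2]) ÷ (1 / √[2(1 − ρ)]) = √[(1 − ρ)/(1 + ρ)]. This is below 1 for every ρ above 0.

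**Power.** If the three-way term has 80% power, its expected z is 1.960 + 0.842 = 2.802. At ρ = 0.5 the ratio is √(0.5/1.5) = 0.577, so the two-way power is Φ(0.577 × 2.802 − 1.960) = Φ(−0.343) = 36.6%. In the same way:

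| ρ (assumed) | z ratio | Two-way power when three-way has 80% | when three-way has 90% |
|---|---|---|---|
| 0 | 1.000 | 80.0% | 90.0% |
| 0.2 | 0.816 | 62.8% | 75.4% |
| 0.3 | 0.734 | 53.8% | 66.2% |
| 0.4 | 0.655 | 45.0% | 56.4% |
| 0.5 | 0.577 | 36.6% | 46.5% |
| 0.6 | 0.500 | 28.8% | 36.7% |
| 0.7 | 0.420 | 21.7% | 27.5% |

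Two-way power falls below half of three-way power only when ρ exceeds about 0.40, 0.46 or 0.51, for three-way power of 50%, 80% or 90%.

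**Link to the planning SDs.** ρ = 1 − SD_change² / (2σ²), and σ is not in the documents. With SD of change 2, assumed σ from 2 to 3 gives ρ from 0.50 to 0.78 and z ratios from 0.58 to 0.35. With SD of change 3, assumed σ from 2.25 to 3 gives ρ from 0.11 to 0.50 and z ratios from 0.89 to 0.58. At σ = 2.5, for example, ρ = 0.28, the ratio is 0.75, and two-way power is Φ(0.75 × 2.802 − 1.960) = 56% against 80%.

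**Simulation check.** 640 participants, a 50:50 factor, SD of change 2, d = 1, and 1,500 simulated trials at each of ρ = 0.2, 0.4, 0.5, 0.6 and 0.7:

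- Complete data: the two-way term recovers 0.50–0.51 of d and the three-way term 1.00–1.02. Two-way power falls from 72% (ρ = 0.2) to 26% (ρ = 0.7); three-way power stays at 88–89%.
- 20% of Week 12 scores missing at random, all available data used: the two-way term recovers 0.41–0.43 of d and the three-way term 0.99–1.01.

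Section 10.6 also says that baseline data stand in for a missing Week 12 score. If that were applied to a random 20%, the three-way term would estimate 0.8d and the two-way term 0.8d/2 = 0.4d, so the ratio would still be one half.

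**More visits.** If the modification is equal at every post-baseline visit, the two-way term recovers (K − 1)/K of it: 2/3 in the three-visit model and 3/4 in the four-visit model.

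**The case against.** The strongest reply is that 10.2.2.2 is shorthand. It speaks of modifying the effect, and 10.2.2.1 defines that effect as β3. Modification of β3 is by definition the three-way term, so a careful analyst would fit it, and nothing in the text excludes it. This stands in part: the plan does not commit to the two-way model, and a reader who infers that the wrong test will certainly be run goes beyond the text. But 10.2.2.1 names intervention × time when it means it, and 10.2.2.2 does not. A test that decides what is reported should name its coefficient.

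The generic wording also has to serve several endpoint types, and here the reply is right. In the Poisson and proportional hazards models the intervention term is itself the effect, so intervention × factor is correct. The composite is defined by change from baseline, so it has no baseline row to dilute it.

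Finally, these are unpowered secondary checks. With 512 analysed, a 50:50 factor and SD of change 2, the three-way standard error is 2 × 2 × √(2/256) = 0.354. Its 80% power point is therefore 0.99 points, about 1.6 times the 0.62 main effect. For a modification of 0.5 points even the three-way term has only Φ(0.5/0.354 − 1.960) = 29% power. That is true and limits the practical gain, but it is no reason to test a diluted quantity.

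**Conclusion.** The point holds for the continuous repeated-measures outcomes. Read literally, the named interaction does not test modification of the 12-week effect. It keeps β3 equal across subgroups, estimates half the modification with two complete visits, and has lower power for any positive ρ: about 63%, 45%, 37% and 22% at ρ = 0.2, 0.4, 0.5 and 0.7, where the three-way term has 80%.

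Two stronger readings are tempting. One is that the test always has less than half the power. That needs ρ above roughly 0.4–0.5, and the documents give neither ρ nor the SD of the score. With SD of change 2 and the assumed score SDs, power is about half or less; with SD of change 3 it is mostly above half. The other is that the estimate is always half, but that fraction is specific to two complete visits.

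The figures assume equal score SDs at both visits and no modification at baseline. The vector of baseline covariates is not itemised; if it includes the baseline score, the power comparison changes. The primary analysis and its conclusion are not affected.

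**What to change.** In Section 10.2.2.2, state that for continuous repeated-measures outcomes effect modification is tested by the coefficient on factor × intervention × I(T = visit of interest), the visit being Week 12, 24 or 36 for Questions 1, 2 and 3. All lower-order terms should be in the model, including factor × time and factor × intervention. Report subgroup-specific effects, such as β3 at each level of the factor, from that same model. State separately that the count and time-to-event models keep intervention × factor. The cost is one or two sentences in the analysis plan, with no new data and no change to the primary analysis.

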10.2.2.3. Missing Data

If missing data are unavoidable, they will be addressed by 1) using models that are valid under the missing at random assumption, and 2) performing sensitivity analyses. The generalized linear mixed effects models are valid under the missing at random assumption. The extent and patterns of missing data will be examined, and logistic regression models will be used to identify factors associated with the missingness. Several approaches will be conducted to address the missingness. First, the generalized linear mixed effects models will further adjust for the identified factors associated with the missingness, compensating for potential violation of the missing at random assumption. Second, the propensity of the missingness, calculated from the above logistic regression, can be used to create inverse weighting in the generalized linear mixed effects models. Sensitivity analyses under missing not at random assumptions (e.g. pattern mixture models) will be conducted to examine the robustness of model-based results.⁶³ For time to event analyses, competing risk models such as cause-specific hazards models or sub-distribution hazards models will be used when there are competing events (e.g., death).

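### Adding predictors of missingness as time-constant main effects does not in general remove dropout bias from the Week 12 difference in change; the factors need visit and arm-by-visit terms

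*Combined protocol and SAP*

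**What the plan says.** Section 10.2.2.1 of the Combined protocol and SAP defines the primary analysis: "The linear mixed effects model will include fixed effects of intervention, time, and interactions between intervention and time". Outcome data are handled jointly: "All repeated measures of the BPI Interference scores at baseline and 12 weeks will be included in the model as the dependent variable". Covariates appear as γᵀW, where W "is a vector of baseline measures, including the stratification factors". W has no visit index and is not multiplied by the Week 12 indicator. The target is β₃: "The primary efficacy estimand is the contrast of PCST and Usual Care for the change at the 12-week time point".

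Section 10.2.2.3 identifies predictors of missingness by logistic regression. Its first remedy is that the mixed-effects "models will further adjust for the identified factors associated with the missingness, compensating for potential violation of the missing at random assumption". No equation is given for this step. Inverse weighting by the missingness propensity comes second, worded as an option. Sensitivity analyses under missing not at random are also planned, with pattern mixture models as the example.

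Section 10.6 separately says that a participant without a Week 12 score will have the baseline score used in its place.

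**The concern.** With both visits as outcomes, γᵀW moves a participant's baseline and Week 12 expectations by the same amount. A factor biases β₃ through dropout mainly by predicting how much the score changes, or how much treatment changes it. A time-constant term has no room for either.

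The setting makes such factors plausible. Treatment is unmasked (Section 4.1). Only PCST carries 12 weekly sessions (Section 6.1). Section 2.2.5.2 links depressive symptoms to non-adherence and hospitalization. Section 10.2.2.2 names depression, anxiety and coping style as possible effect modifiers. If one of these drives loss, the adjusted estimate stays biased, although the plan describes it as having compensated for the problem.

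**Working it through.** **1. The plan's own figure.** Section 10.2.1 uses "a power of 90%, a type 1 error of 5%, an attrition rate of 20%, standard deviations of change of 2 and 3", and Section 10.2.2 specifies analysis "using two-sided statistical tests and confidences intervals". With 640 participants, an interim inflation factor of 1.173 and ICC 0:

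- n per arm = 320 × 0.8 / 1.173 = 218.2
- detectable difference = (1.960 + 1.282) × 2 × √(2/218.2) = 0.62

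This matches Table 10.2, row 2. The documents give no figure for dropout bias, so what follows rests on stated assumptions.

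**2. What the model does with a dropout.** Let F be a centred baseline factor with slope b0 on the baseline score and slope b1 on the change. Let ρ be the within-person correlation given F. For someone with only a baseline score, the fitted model predicts Week 12 as the arm mean + γF + ρ × (baseline residual). The slope of predicted change on F among dropouts, where the truth is b1, is:

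- F omitted: −(1−ρ)b0
- F as a main effect: (1−ρ)(γ−b0)
- F and F × visit: b1, which is correct

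γ is a compromise. Completers carry information 2/(1+ρ) and point to b0 + b1/2; dropouts carry information 1 and point to b0. With 20% lost, (γ−b0)/b1 ≈ 0.8 / (1.6 + 0.2(1+ρ)). At ρ = 0.5 this is 0.8/1.9 = 0.42, so dropouts are credited with about 0.5 × 0.42 = 21% of the true slope. b0 cancels, so the bias left after main-effect adjustment does not depend on the factor's link to baseline score. The unadjusted bias does.

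**3. Hand check, binary factor (assumed).** Prevalence is 50% and b1 = 1. Dropout is 20% at both levels in Usual Care, and 5% (F absent) or 35% (F present) in PCST.

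- F among PCST completers: 0.65/(0.95 + 0.65) = 0.406, against 0.500 in Usual Care
- Bias without F, at b0 = 0: (0.406 − 0.500) × 1 = −0.094
- Bias with F as a main effect, at ρ = 0.5: −0.094 × (1 − 0.21) = −0.074. The large-sample maximum-likelihood fit gives −0.073.
- Bias with F × visit: 0.000

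**4. Illustration, continuous factor.** From the plan: 20% attrition (taken in each arm) and SD of change 2. Assumed: F standard normal, b1 = 0.6, and dropout odds ratio 2 per SD in PCST with random loss in Usual Care. Numerical integration puts mean F among PCST completers at −0.129, so the bias at b0 = 0 without F is 0.6 × (−0.129) = −0.077. Large-sample limits of the fitted model, omitting the site effect:

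| ρ | No F, b0 = −0.5 / 0 / 0.5 / 1 | F main effect (any b0) | F × visit | Share removed by main effect (same b0 order) |
|---|---|---|---|---|
| 0.3 | −0.030 / −0.077 / −0.116 / −0.137 | −0.053 | 0.000 | −75% / 31% / 54% / 61% |
| 0.5 | −0.043 / −0.077 / −0.107 / −0.126 | −0.060 | 0.000 | −39% / 22% / 44% / 52% |
| 0.7 | −0.057 / −0.077 / −0.096 / −0.111 | −0.067 | 0.000 | −19% / 13% / 30% / 39% |

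The remaining bias is about 0.05 to 0.07 points: 0.05/0.62 = 8% and 0.07/0.62 = 11%. Here it exaggerates the benefit; reversing the factor's direction reverses the sign.

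**5. Effect modifier lost equally in both arms.** The odds ratio is 2 in each arm and the effect varies by 0.6 points per SD. The bias is 0.6 × (−0.129) = −0.077 without F, with F as a main effect, and with F × visit. It is zero only with F × arm × visit, F centred.

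**6. Cases with nothing to fix.** If dropout depends on F equally in both arms and F does not modify the effect, the bias is zero in every fit. If F predicts level but not change, the main effect removes all of it.

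**7. If Section 10.6 is applied.** Everyone then has two scores, β₃ is the difference in mean change, and γF cancels within each person. The main effect changes β₃ by nothing. A mixed-model check on simulated data gave identical estimates with and without F.

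**The case against.** Main-effect entry is an inference, because Section 10.2.2.3 writes no equation for this step. It is still the natural reading: the section extends the Section 10.2.2.1 model, and no interaction is mentioned.

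The plan also has other safeguards: optional inverse weighting, sensitivity analyses under missing not at random, withdrawal comparisons by arm (Section 10.6) and treatment-by-factor interactions (Section 10.2.2.2). Weighting could address this bias but is not firmly committed to. The others answer different questions or do not correct β₃.

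The size is modest. With 256 completers per arm and SD 2, the standard error is 2 × √(2/256) = 0.18, so 0.06 points is about a third of it. The illustration also needs factor-driven loss in one arm and random loss in the other. Both points stand, and they limit the importance of the concern.

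Three stronger readings are tempting, and none is supported:

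- **The remedy always removes about one fifth of the bias.** That share holds only when the factor is unrelated to baseline score and ρ is near 0.5. Elsewhere it can be about half, all, or negative. The documents give neither ρ nor that link, and Section 2.1 says depression can worsen chronic pain, so no link is not a natural default for depression.
- **Only loss that differs by arm matters.** Step 5 shows otherwise.
- **Adjusted and unadjusted results will always agree and so mislead.** At ρ = 0.5 and b0 = 0.5 the bias moves from −0.107 to −0.060, a visible shift. Agreement is automatic only under the Section 10.6 rule.

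**Conclusion.** The concern holds as a limited one. As the model is written, adjusting for predictors of missingness does not in general remove dropout bias from β₃ when the factor predicts change and drives loss differently by arm, or when it modifies the effect and drives loss in either or both arms. Under the step 4 assumptions about 0.05 to 0.07 points remain; under step 5, about 0.08. These sizes depend on an assumed factor strength, dropout odds ratio and correlation, none of which the documents give.

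The claim of compensating for a violation of missing at random is also too strong. Conditioning on observed factors makes that assumption more plausible; it does not address its failure. This is a supporting analysis, so the change is advisable rather than essential to the primary result.

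**What to change.** In Section 10.2.2.3:

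- State that baseline factors associated with missingness will be centred and entered with factor × visit and factor × arm × visit terms. Include the latter whenever effect modification is plausible, not only where missingness differs by arm. Centring keeps β₃ as the average effect. Multiple imputation by arm, with these factors as predictors of the Week 12 score, is an acceptable alternative.
- Replace the claim of compensation with *making the missing at random assumption more plausible*.
- Reconcile this section with the Section 10.6 substitution of baseline for a missing Week 12 score, and say which rule governs the primary analysis. Until that is settled, the adjustment may have no effect on β₃ at all.

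The cost is a few sentences, some degrees of freedom and a slightly wider interval in a supporting analysis.
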